#### 5.3.1 Description

Ipilimumab is a sterile, preservative-free, clear to slightly opalescent, colorless to pale yellow solution of IV infusion, which may contain a small amount of visible translucent-to-white, amorphous ipilimumab particulates. It is supplied in single-use vials of 50 mg/10mL and 200 mg/40 mL.

#### 5.3.2 Packaging and Labeling

Primary Packaging (Volume)/Label type: Carton of 6 (50 mg/10 mL) or 4 vials (200 mg/40 mL)

#### 5.3.3 Storage and Handling

Store ipilimumab under refrigeration at 2C to 8C (36F-46F) in the original package until time of use. Protect from light. Do not freeze.

Store the diluted solution for no more than 24 hours under refrigeration 2 to 8C (36 to 46F) or at room temperature 20^0 to 25C (68 to 77F).

#### 5.3.4 Dose, Schedule and Administration

See section 5.3.4

The recommended dose of ipilimumab for metastatic melanoma is 3mg/kg administered over 90 minutes every 3 weeks for a maximum of 4 doses. The recommended dose for adjuvant treatment of melanoma is 10 mg/kg administered over 90 minutes every 3 weeks for 4 doses followed by 10mg/kg every 12 weeks for up to 3 years.

In this trial, ipilimumab will be given at a dose of 1mg/kg administered over 30 minutes every 6 weeks if DL1 is tolerated as outlined in the study schema and described in section 4.3.

#### 5.3.5 Preparation

See the ipilimumab prescribing information for preparation instructions. Do not shake the product. Inspect for particulate matter or discoloration prior to administration. Discard vial if solution is cloudy, there is pronounced discoloration (solution may have pale yellow color) or there is foreign particulate matter other than translucent-to-white, amorphous particles.

#### 5.3.6 Stability

Store the diluted solution for no more than 24 hours under refrigeration 2 to 8C (36 to 46F) or at room temperature 20^0 to 25C (68 to 77F).

### 5.3.7 Return and Retention of Ipilimumab

Unused vials will be handled per instructions from BMS. Partially used and completely used vials will be destroyed per institutional guidelines.

### 5.3.8 Adverse Events Associated with Ipilimumab

The adverse events noted here have been reported in subjects receiving ipilimumab. See section 4.4.3 for further instruction on the management of adverse events associated with ipilimumab in combination with nivolumab therapy.

- Common adverse events occurring in  $\geq 5\%$  of subjects on ipilimumab are fatigue, diarrhea, pruritus, rash, and colitis.
- Additional common adverse reactions at the 10mg/kg dose ( $\geq 5\%$ ) include nausea, vomiting, headache, weight loss, pyrexia, decreased appetite, and insomnia.
- Other events may occur. One event that has been observed is hemolytic anemia

### 5.4 Return and Retention of Study Drug

The investigator is responsible for keeping accurate records of the clinical supplies received from the study, the amount dispensed to the subjects and the amount remaining at the conclusion of the trial.

Upon completion or termination of the study, all unused and/or partially used and completely used vials of investigational product will be destroyed per UNC IDS drug destruction policy for drug received by UNC. All unused drug will be handled per instructions provided by the manufacturer. In general, it is the Investigator's responsibility to arrange for disposal of all empty containers, provided that procedures for proper disposal have been established according to applicable federal, state, local and institutional guidelines and procedures, and provided that appropriate records of disposal are kept.

## 6.0 EVALUATIONS AND ASSESSMENTS

### 6.1 Time and Events Table

Assessment	Pre-Study 	D1  Cycle 1	D15  Cycle 1	D29  Cycle 1	D1  Cycle 2	D15  Cycle 2	D29  Cycle 2	D1  Cycle 3-N	D15  Cycle 3-N	D29  Cycle 3-N	End of Treatment 	30-day Follow up 	100-day Follow up 	Long term Follow up 
Informed Consent	X													
History 	X	X	X	X	X	X	X	X	X	X	X	X		
Physical exam	X	X	X	X	X	X	X	X	X	X	X	X		
Performance Status	X	X	X	X	X	X	X	X	X	X	X			
Tumor measurement 	X							X 						
Pregnancy test 	X	X 			X 			X 			X 	X 		
Hematology 	X	X	X	X	X	X	X	X	X	X	X			
Serum Chemistries	X	X	X	X	X	X	X	X	X	X	X			
TSH, Free T3/T4 	X				X			X			X			
ACTH/Amylase/Lipase 	X				X			X			X			
CEA 	X				X			X			X			
Toxicity Assessment	X	X	X	X	X	X	X	X	X	X	X	X	X	X
Concomitant Meds 	X	X	X	X	X	X	X	X	X	X	X	X		
Ipilimumab IV (if DL1 safe) 		X			X			X						
Nivolumab IV 		X	X	X	X	X	X	X	X	X				
Panitumumab IV 		X	X	X	X	X	X	X	X	X				
Request archival or Perform mandatory biopsy	X 													
Blood sample 		X			X			X			X			
Stool specimen	X							X 						
On treatment Tumor biopsy (Optional; goal n=15)	X			X 										
Survival analysis													X	X

1. Radiological assessments and physical exam may be performed within 4 weeks prior to day 1 of treatment. Other evaluations except for pregnancy test must be performed within 3 weeks prior to Cycle 1 Day 1 (C1D1) of treatment. Serum or urine  $\beta$ -HCG must be performed **within 24 hours prior** to first dose of study medication for women of child-bearing potential. Other screening labs performed within 72 hours prior to Cycle 1 Day 1 do not need to be repeated on C1D1.
2. Treatment cycles are to be repeated every 42 days until progression. A window of +/- 3 days applies to all study visits unless otherwise specified. While the treatment window is +/- 3 days, a minimum of 12 days must pass before the next dose of nivolumab.
3. The end of treatment visit should only occur when subjects permanently stop study treatment. Subjects who have an ongoing  $\geq$  grade 2 or serious AE (SAE) at this visit will continue to be followed until the event is resolved or deemed irreversible by the investigator. The 30-day (+/- 7 days) follow up visit after stopping study treatment should be performed to check for ongoing toxicity. Subsequently, subjects should be contacted by telephone at approximately 100 days (+/- 7 days) after discontinuing study treatment for the emergence of SAEs (including checking for pregnancy) and to ensure contraceptive guidelines are followed as stipulated in inclusion criteria 3.1.11 and 3.1.12. Subsequent long-term follow-up for survival, defined as every 90 days thereafter (+/- 15 days) for up to 3 years or until death (whichever is first) may be conducted via telephone or chart review and/or clinic visit. Long term survival follow up will be limited to history of any subsequent cancer treatments, an assessment of any SAEs (including checking for pregnancy) considered to be possibly or probably related to study treatment until resolution, and survival status.
4. Complete history at baseline only, thereafter focused history on symptoms/toxicity; physical exam to include height (baseline only), examination of the skin, weight, and vital signs. Note that starting with cycle 7, only include assessment by physician on days 15 and 29 if clinical signs and symptoms warrant MD consult
5. Tumor imaging should remain consistent throughout study and should include those thought by investigator to best capture status of disease. Disease assessments should include contrasted computed tomography (CT) of the chest and either contrasted CT of abdomen and pelvis or MRI of abdomen and pelvis. Repeat tumor imaging every 12 weeks (+/- 1 week).
6. Urine or serum  $\beta$ -HCG must be performed within 24 hours prior to first dose of study medication for women of child-bearing potential. The test result must be confirmed as negative prior to dosing with study medication. A serum or urine pregnancy test must be repeated every 6 weeks while receiving study medications and repeated approximately 30 days after discontinuing the study medications.
7. Hematology: CBC with differential including Hgb, and platelet count. Serum chemistries will include a complete metabolic panel (ie, BUN, creatinine, sodium (Na), potassium (K), Chloride (Cl), Bicarbonate (CO2), glucose, calcium (Ca), albumin, total protein, total bilirubin, ALT, AST, and alkaline phosphatase) + magnesium (Mg) and phosphorus.
8. Thyroid function test: TSH and free T3/T4 should be assessed prior to initiating study treatment and performed every 6 weeks +/- 3 days during study treatment and at the end of treatment. ACTH, amylase and lipase should be measured at baseline (pre-study) and

- then on D1 of each cycle. CEA should be measured pre-study and then on D1 of each cycle.
9. Please note all subjects should receive prophylaxis for panitumumab-associated rash with a tetracycline antibiotic (like doxycycline or minocycline) and continue for at least the duration of the first cycle of study combination treatment (i.e., 6 weeks), as described in section 4.5.1
  10. Ipilimumab dosing will be halted and will not be given if the triple combination is determined to be unsafe during the safety run-in period (Cohort 1). If this is the case then subjects will be dosed with panitumumab and nivolumab in (Cohort 2) as described in section 4.3.2
  11. Fixed paraffin-embedded blocks or slides from the original diagnostic specimen or from a metastatic or recurrent site must be requested for subjects at baseline. Subjects with inadequate archival specimens must undergo a mandatory biopsy prior to initiating study medications.
  12. Blood samples will be collected for correlative studies on D1 of each cycle prior to dosing, and at the end of treatment visit.
  13. Stool specimen should be collected +/- 7 days from C3D1.
  14. We will collect fresh on-treatment biopsies (optional) in consenting patients for correlative studies in up to 15 patients. The on-treatment biopsy will be performed during cycle 1 on or between days 28 and 35.

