### 2.4.2 Secondary Endpoints

**2.4.2.1** The best overall responses for both RECIST 1.1 and irRECIST are defined as the best response achieved across all time points prior to progression (for example, a subject who has SD at first assessment, PR at second assessment, and PD on last assessment has a best overall response of PR). Please Note: In the case of SD, measurements must have met the SD criteria at least once after study entry at a minimum interval of 12 weeks from initiation of treatment.

**2.4.2.2** The immune-related response rate is defined as the percentage of subjects with unresectable refractory *KRAS/NRAS/BRAF* wild-type MSS mCRC who achieve a CR+PR by 12 weeks to panitumumab/nivolumab/ipilimumab or panitumumab/nivolumab therapy per irRECIST criteria. (See section 6.7.5.1)

**2.4.2.3** Assessment of immune-related PFS is defined as starting from the first day of treatment or Day 1 (D1) until the event of disease progression as defined by irRECIST, or death from any cause in subjects with unresectable refractory *KRAS/NRAS/BRAF* wild-type MSS mCRC (See section 6.7.5.1). Any subject that has not had a documented event at the time of analysis will be censored. Assessment of PFS (as defined by RECIST 1.1) is defined from D1 of treatment until the event of disease progression occurs or death from any cause in subjects with unresectable refractory *KRAS/NRAS/BRAF* wild-type MSS mCRC. Any

October 01,,  
2020

subject that has not had a documented event at the time of analysis will be censored.

- 2.4.2.4 OS is defined as the time from D1 of treatment until death from any cause. Any subject that has not died by the analysis date will be censored.
- 2.4.2.5 The duration of response as defined by RECIST 1.1 will be defined as the time elapsed from first scan documenting partial response or complete response until the event of disease progression occurs. Any subject that has not had a documented progression at the time of analysis will be censored. The duration of response as defined by irRECIST will be defined as the time elapsed from first scan documenting partial response or complete response until the event of disease progression occurs. Any subject that has not had a documented progression at the time of analysis will be censored.
- 2.4.2.6 Treatment-related adverse events will be assessed per NCI-CTCAE v4.03.

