## 4.0 TREATMENT PLAN

### 4.1 Schema

#### 4.1.1 Rationale for Doses Selected

We plan to perform a single-arm, open-label, multicenter Phase II clinical trial of nivolumab 240 mg IV q2wk, ipilimumab (1 mg/kg IV q6wk), and panitumumab (6 mg/kg IV q2wk), after a safety lead-in cohort of a total of 6 subjects has completed 12 weeks of combination therapy at the proposed starting doses. The starting doses and schedule were carefully selected after consideration of existing clinical studies and preclinical data. The efficacy of ipilimumab monotherapy is dose-dependent, but the rate and severity of immune-related adverse events is also dose-dependent. The FDA-approved dose of combination ipilimumab and nivolumab in management of metastatic melanoma is ipilimumab 3 mg/kg IV q3wk for four doses combined with nivolumab 1 mg/kg IV q3wk; followed by nivolumab monotherapy 240 mg flat dose IV q2wk. Notably, studies of combination ipilimumab and nivolumab have started both antibodies concurrently, with the rationale that preclinical models showed that the combination is synergistic only when administered concurrently rather than sequentially, and so we plan to administer the investigational drugs concurrently as well. Subsequent clinical trials have investigated combinations of ipilimumab and nivolumab that would attenuate the frequency and severity of immune-related adverse events without mitigating efficacy. The efficacy and toxicity profiles of more infrequent dosing of ipilimumab combined with nivolumab were studied in a phase I study in subjects with chemotherapy-naïve recurrent stage IIIB or IV NSCLC, CheckMate 012. In this study, treatment with ipilimumab 1 mg/kg q6wk combined with nivolumab 3 mg/kg q2wk was much better tolerated than treatment with ipilimumab 1 mg/kg q3wk combined with nivolumab 3 mg/kg q3wk. Additional dosing combination regimens tested revealed inferior efficacy when nivolumab dosing was decreased to 1 mg/kg. Treatment with ipilimumab 1 mg/kg q6wk combined with nivolumab 3 mg/kg q2wk resulted in a 33% rate of grade 3-4 treatment-related AEs, but only 13% rate of treatment-related AEs leading to study drug discontinuation (compared to 19% grade 3-4 treatment-related AEs and 10% treatment-related AEs leading to discontinuation in nivolumab 3 mg/kg IV q2wk arm). The FDA has determined that based on population pharmacokinetics models, there is a negligible difference in overall exposure between nivolumab 240 mg IV q2wk and 3 mg/kg IV q2wk. Consequently, we plan the ipilimumab and nivolumab dosing within safety cohort 1 to be ipilimumab 1 mg/kg IV q6wk plus nivolumab 240 mg IV q2wk. The dose of panitumumab selected within dose level 1 is the FDA-approved monotherapy dose.

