  - Grade 4 drug-related endocrinopathy adverse events, such as adrenal insufficiency, ACTH deficiency, hyper- or hypothyroidism, or glucose intolerance, which resolve or are adequately controlled with physiologic hormone replacement (corticosteroids, thyroid hormones) or glucose-controlling agents, respectively, may not require discontinuation after discussion with and approval from the Investigator
- Any dosing interruption lasting > 6 weeks with the following exceptions:
  - Dosing delays or interruptions to allow for prolonged steroid tapers to manage drug-related adverse events are allowed. Prior to re-initiating treatment in a subject with a dosing interruption lasting > 6 weeks, the Investigator must be consulted. Tumor assessments should continue as per protocol even if dosing is interrupted or delayed
  - Dosing interruptions or delays lasting > 6 weeks that occur for non-drug-related reasons may be allowed if approved by the Investigator. Prior to re-initiating treatment in a subject with a dosing interruption lasting > 6 weeks, the Investigator must be consulted. Tumor assessments should continue as per protocol even if dosing is interrupted
- Any adverse event, laboratory abnormality, or intercurrent illness which, in the judgment of the Investigator, presents a substantial clinical risk to the subject with continued nivolumab and ipilimumab dosing

Additionally, after any immune related adverse event that does not meet the mandatory discontinuation requirement, the treating investigator should carefully consider the safety of resuming nivolumab and/or ipilimumab. In select cases, like for colitis, it would be appropriate to discontinue ipilimumab but continue nivolumab. This should be discussed with the medical monitor, and decisions should use guidelines for rechallenge after immune-related adverse events, such as found in the NCCN Management of Immunotherapy-Related Toxicities Version 1.2020.

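### No tumor assessment or progression date is planned once a subject stops all treatment without progression, yet any later death counts as a PFS event and no censoring date is given.

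*Combined protocol and SAP*

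**What the plan says.** **Assessments.** The Time and Events Table (6.1) marks tumor measurement at Pre-Study and on D1 of Cycle 3-N only. The columns for end of treatment, 30-day, 100-day and long-term follow-up are blank. Sections 6.4.1 to 6.4.4 agree: none lists imaging or progression status. Footnote 3 of 6.1 says "Long term survival follow up will be limited to history of any subsequent cancer treatments", together with related SAEs and survival status, and 6.4.4 repeats the restriction. Section 4.7 gives OS as the purpose of this follow-up.

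**PFS.** Section 2.4.2.3 has PFS by RECIST 1.1 "defined from D1 of treatment until the event of disease progression occurs or death from any cause". The only censoring rule is "Any subject that has not had a documented event at the time of analysis will be censored". It gives no date at which to censor and no rule for missed assessments or new anticancer therapy. The irRECIST version has the same structure. Section 8.4 adds only the Kaplan-Meier method, log-log intervals and, if appropriate, 6-, 12- and 24-month estimates.

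**Duration of response.** Section 2.4.2.5 defines it as "time elapsed from first scan documenting partial response or complete response until the event of disease progression occurs", and "Any subject that has not had a documented progression at the time of analysis will be censored". Death is not an event.

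**The concern.** Unacceptable adverse events are a listed reason to end therapy (4.6), so some subjects will leave all treatment before progressing. From then on a progression has no planned route into the data, but a death does. Someone who stops for toxicity, progresses a few months later, starts another regimen and dies at month 20 would be recorded as having 20 months of PFS.

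PFS and duration of response are named secondary objectives (2.2.3, 2.2.5). There is one arm, so the error cannot cancel against a control. A progression date that was not collected at the time may be hard to recover later.

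**Working it through.** **The plan's own figures.** The documents give no PFS or duration-of-response assumption to reproduce. Their only design figures are for ORR. An exact binomial calculation of the Simon rule in 8.2 (continue with at least 7 of 32, succeed with at least 17 of 56; 22% vs 35%) gives alpha 0.090 and power 0.801, as stated. That rule uses response by 12 weeks and no PFS data.

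**Inputs**
- Scan interval: 12 weeks = 84/30.44 = 2.76 months (6.1 footnote 5; 6.3.5). The last scan before month 12 is at 4 × 2.76 = 11.04 months.
- Share stopping all treatment before progression: q = 13%, 20% or 35%. Section 4.1.1 cites "only 13% rate of treatment-related AEs leading to study drug discontinuation", but for nivolumab plus ipilimumab in lung cancer, without panitumumab. The 35% is the rate above which 8.3 calls toxicity unacceptable. The 20% is an intermediate assumption.
- Assumed, not in the documents: exponential times; median time to progression 4 or 6 months; median 8 months from progression to death; stopping unrelated to prognosis; 36-month cut-off.

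**Formulas.** Let p = ln 2/(median time to progression), s = p·q/(1−q) for stopping, and d = ln 2/8 = 0.0866 for death after progression.
- Progression captured: PFS(12) ≈ exp(−11.04p).
- As written: PFS(12) ≈ (1−q)·exp(−11.04(p+s)) + q·P(T > 12). T is the time to death for a stopped subject, the sum of three exponential stages with rates p+s, p and d.

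**Worked case** (median 4 months, q = 35%). p = 0.1733, s = 0.0933, p+s = 0.2666.
- Captured: exp(−0.1733 × 11.04) = 0.148.
- Not stopped: 0.65 × exp(−0.2666 × 11.04) = 0.65 × 0.0527 = 0.034.
- Stopped: P(T > 12) = 0.0365 − 0.3571 + 1.0475 = 0.727, and 0.35 × 0.727 = 0.254.
- As written: 0.034 + 0.254 = 0.289 before rounding of the parts, an excess of 14 points.

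**All six cases**, by simulation of 200,000 subjects each. The formulas agree to within 0.3 points.

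| Median PFS | Stopping | 12-month PFS, progression captured | 12-month PFS, as written | Excess (points) |
|---|---|---|---|---|
| 4 mo | 13% | 14.5% | 19.3% | 4.8 |
| 4 mo | 20% | 14.6% | 22.3% | 7.7 |
| 4 mo | 35% | 14.7% | 28.9% | 14.2 |
| 6 mo | 13% | 27.8% | 31.1% | 3.3 |
| 6 mo | 20% | 27.9% | 33.1% | 5.2 |
| 6 mo | 35% | 27.9% | 38.0% | 10.1 |

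The median stayed on the same scan date in all six. With a median time to progression of 8 months it could move from 8.3 to as much as 11.0 months, one scan interval.

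**Dependence on the unstated censoring date.** The table treats stopped survivors as progression-free to the cut-off. If they are instead censored at their last scan while deaths still count, the excess is about 2 to 4 points at 13% stopping and about 7 to 12 at 35%. If every stopped subject is censored at the last scan and later deaths are ignored, the sign reverses, to about −1 to −5 points (medians 4 to 8 months).

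**Duration of response.** No arithmetic is needed. Progression after the stop is not seen and death does not count, so a responder who stops all treatment can only be censored, at a date the plan does not give.

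**The case against.** **Does the text already cover this?** Section 4.4.2.5 says "Tumor assessments should continue as per protocol even if dosing is interrupted or delayed", but that concerns interruptions after which dosing may resume, not a permanent stop. Footnote 5 of 6.1 repeats imaging every 12 weeks without naming an end. Sections 4.7 and 4.8 speak of follow-up as stipulated and of further scheduled assessments, but no off-treatment scan is scheduled for them to refer to. Section 4.1.1 gives a 6-week interval, which conflicts with the 12 weeks in 6.1 and 6.3.5 and must be reconciled. It does not extend past treatment either. A reader might infer that scans after stopping are forbidden, or that progression can never be known. The documents do not go that far: they are silent on scans, chart review is allowed, and later cancer treatments are recorded. No rule uses that information for PFS.

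**Are the stop rates too high?** Partly. Discontinuation is often of one agent: panitumumab alone (4.4.1), ipilimumab with nivolumab continued (4.4.2.5), or the offending antibody (4.5.2). Such subjects may still be scanned, so it would be wrong to read every toxicity stop as affected. Nor is 35% an expected rate, and the top of the range depends on it.

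**Do the later deaths also distort duration of response?** A reader might infer so. They do not, because death is not an event in 2.4.2.5.

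**Does it matter?** PFS is secondary and descriptive, with no PFS hypothesis. With 56 subjects and no censoring, the 95% half-width is about 1.96 × √(0.15 × 0.85/56) = 9 points at 15%, and 12 points at 28% by the same formula. A 3- to 5-point shift lies inside that. This limits the severity. It does not excuse a systematic error that is cheap to prevent.

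**Conclusion.** The gap is real for subjects who permanently stop all study treatment without progression. Applied as written, the PFS definition scores unrecorded progression followed by death as long PFS. Twelve-month PFS is then overstated by about 3 to 14 points, or about 2 to 12 if stopped survivors are censored at their last scan.

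These sizes rest on assumed progression, survival and stopping rates, and on stopping being unrelated to prognosis. The plan fixes neither the size nor, across the censoring choices an analyst might make, the direction. That is itself a reason to state the rule. The effect on duration of response is a separate censoring problem and is not quantified here. The ORR sample size and decision rule are unaffected. The change should be made, but the trial does not depend on it.

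**What to change.** 1. **Follow-up content (6.1 footnote 3 and 6.4.4).** For subjects who stop without progression, add to the existing follow-up contacts the date of progression from standard-of-care imaging or the clinical record, and the start date of any new anticancer therapy.
2. **Censoring (2.4.2.3 and 2.4.2.5).** State that subjects without an event are censored at the last adequate tumor assessment. Say explicitly whether death ends a response.
3. **Sensitivity analysis.** Report PFS that also censors at the last assessment before new therapy, or before a death that follows two or more missed assessments. Whether such deaths count is partly a choice of estimand, so both results should be shown.

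**Cost.** Two fields at contacts already made by telephone, chart review or visit, one of which overlaps with the treatment history already collected; a few sentences; one extra analysis. No scans or visits are added.

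**Downsides.** Routine scans are less regular than protocol scans. Where no routine scan exists, the sensitivity censoring can understate 12-month PFS, by about 1 to 4 points in these scenarios. A stricter coding, in which a death counts only within two scan intervals of the last scan and all other stopped subjects are censored there, gave 1.6 to 5.6 points. The exact coding should therefore be written down.
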